### **5.10.1. Discontinuation from Study Treatment**

Patients may be withdrawn from study treatment at any time at their own request, or they may be withdrawn at the discretion of the Investigator or Sponsor for safety or non-compliance to the protocol.

Reasons for permanent discontinuation of both study drugs may include the following:

- Radiological PD
- Clinical progression
- Withdrawal of consent to study treatment, but agrees to the protocol-defined follow up

- AE
- Investigator decision
- Study terminated by Sponsor
- Major protocol deviation or non-compliance
- Patient becomes pregnant
- Death
- Other

Depending on the disease state and the tumor response, patients who permanently discontinue study treatment will enter into the response and survival follow-up portion of the study: patients who had discontinued study treatment due to PD will be followed-up for survival every 12 weeks ( $\pm$  4 weeks) for up to one year from the last patient's first dose (Cycle 1 Day 1); Patients who discontinued the treatment for reasons other than PD (including treatment completion) will be followed by radiographic assessment every 12 weeks ( $\pm$  4 weeks) from the time of the patient's last on-study tumor assessment until documentation of PD or beginning of subsequent anti-cancer therapy (regimen and start date to be recorded in the EDC). After the response follow-up, patients will enter into the survival follow-up. Patients will not be required to visit the clinic for survival follow-up.

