10.4 Extent of Exposure

Debio 1562 will be given intravenously:

- On day 1 of each 21-day cycle for subjects assigned to a Debio 1562 Q3W dosing schedule cohort. Planned Debio 1562 dose for the Q3W dosing schedule is 0.7 mg/kg;
- On day 1, day 8 and day 15 of each 21-day cycle for subjects assigned to the Debio 1562 QW dosing schedule cohort. Planned Debio 1562 dose for the QW dosing schedule is 0.4 mg/kg, 0.2 mg/kg and 0.2 mg/kg at day 1, day 8 and day 15 of each cycle.

Rituximab will be given intravenously on day 1 of each 21-day cycle after the infusion of Debio 1562. Planned dose for rituximab is 375 mg/m².

For Debio 1562, the total dose of drug will be calculated based on each subject's body weight. The weight used for calculation should be obtained prior to first treatment and thereafter should only be modified for relevant ($\geq 10\%$) changes in baseline body weight (not influenced by weight gain or loss attributed to fluid retention).

The exposure to Debio 1562 and rituximab will be summarized by cohort and overall, with summary statistics including mean, standard deviation, median, minimum, and maximum on:

- **Number of treatment cycles**, defined as the number of cycles in the eCRF where non-zero dose of Debio 1562 was infused;
- **Treatment duration**, expressed in weeks. It is calculated as:
$$\text{Ceiling} ((\text{date of last cycle day 1} - \text{date of first dose} + 21) / 7);$$
- **Total cumulative dose**, expressed in mg. It is calculated as the sum of the actual dose administered in all cycles while the subject is on study drug;
- **Actual dose level**:
 - o Debio 1562 actual dose level, expressed in mg/(kg*cycle). It is calculated as:
$$\text{Total cumulative dose of Debio 1562 (mg)} / (\text{average pre-dose weight (kg)} * \text{number of cycles})$$
 - o Rituximab actual dose level, expressed in mg/(m²*cycle). It is calculated as:
$$\text{Total cumulative dose of rituximab (mg)} / (\text{average pre-dose Body Surface Area (BSA) (m}^2\text{)} * \text{number of cycles})$$

Relative dose intensity per week (over the treatment duration)

- **Relative dose intensity per week**, expressed in %. It is calculated as: $\text{Actual dose intensity} / \text{planned dose intensity} * 100$
- **Actual dose intensity**, expressed in mg/week. It is calculated as:
$$\text{Total cumulative dose (mg)} / \text{duration of dosing (weeks)}.$$
- **Planned dose intensity**, expressed in mg/week. It is calculated as

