$$\text{Total planned cumulative dose in a cycle (mg/kg or mg/m}^2\text{)} * \text{pre-dose weight (kg) or BSA (m}^2\text{)} / 3 (\text{weeks})$$

The pre-dose weight used for this calculation should be obtained prior to first treatment, i.e. at Cycle 1 Day 1, and thereafter should only be modified for significant ($\geq 10\%$) changes in body weight.

Relative dose intensity (Listing)

- **Relative dose intensity**, expressed in %. It is calculated as: actual cumulative dose received / planned cumulative dose during the same number of cycles * 100, where:
- **The number of cycles** for this calculation will be taken as the number of initiated cycles up
- to Cycle 6 included, or until PD, or until decision to end the treatment, whichever comes first.
- **The actual cumulative dose received** will be calculated as the sum of doses that have been administered during the above-defined number of cycles.
- **The planned cumulative dose** will be calculated as the planned per protocol dose (for Debio 1562: 0.8 mg/kg for Cohort B, 0.7 mg/kg for all other cohorts; for rituximab: 375 mg/m²) multiplied by the number of cycles initiated (up to Cycle 6 or until PD, or until decision to end the treatment, whichever comes first).

The number and percentage of subjects who had interrupted, missed, delayed, or decreased dosing, and the reason(s) will be summarized for Debio 1562 and rituximab. For each modification action, each distinct reason will be reported in each specific category.

Supportive by-subject listings of Debio 1562 and rituximab infusions will be presented.

Infusion rate will be obtained from the relevant data in the EDC but also calculated as (mg in infusion)/(time of treatment end – time of treatment start). Both will be presented in listings.

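### The listed relative dose intensity in SAP 10.4 counts a full 0.8 mg/kg for the last QW cycle even when treatment ends before Day 8 or Day 15, so a compliant Cohort B patient can look under-dosed

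*SAP*

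**What the plan says.** SAP 10.4 (Extent of Exposure) defines two relative dose intensities.

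- **Listing version.** The numerator "will be calculated as the sum of doses that have been administered during the above-defined number of cycles". The denominator is the protocol dose per cycle, "0.8 mg/kg for Cohort B, 0.7 mg/kg for all other cohorts", "multiplied by the number of cycles initiated (up to Cycle 6 or until PD, or until decision to end the treatment, whichever comes first".
- **Weekly version.** Actual intensity is cumulative dose over a duration of dosing in weeks. Planned intensity starts from the "Total planned cumulative dose in a cycle", multiplied by weight and divided by 3 weeks. The sub-heading ties this version to the treatment duration, which the same section defines as running from first dose to Day 1 of the last cycle plus 21 days, rounded up to whole weeks.

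The two schedules differ within the cycle. For QW, the planned dose is "0.4 mg/kg, 0.2 mg/kg and 0.2 mg/kg at day 1, day 8 and day 15 of each cycle". For the other schedule, "Planned Debio 1562 dose for the Q3W dosing schedule is 0.7 mg/kg", all of it on Day 1. Protocol 5.10.1 allows treatment to stop mid-cycle: "Patients may be withdrawn from study treatment at any time at their own request". Radiological or clinical progression and death are among the other reasons it lists.

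**The concern.** The denominator is built from whole cycles. That suits a regimen that gives its full cycle dose on Day 1, because an initiated cycle is then a fully dosed cycle. It does not suit a regimen in which half the dose falls due later. The reference to PD or the decision to stop does not help: a cycle begun before that date is already initiated and counts in full.

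The consequence is that two situations become indistinguishable in Cohort B's figure: a dose that was due and not given (for example a Day 8 or Day 15 dose skipped under Protocol 5.9.1), and a dose that never fell due because treatment had ended. Protocol 1.6 presents the QW schedule as lowering the peak while maintaining overall exposure, so readers will look at how much of the planned dose was delivered and will compare the two cohorts on it.

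**Working it through.** **Inputs** (all SAP 10.4): QW doses 0.4, 0.2 and 0.2 mg/kg on Days 1, 8 and 15; Q3W dose 0.7 mg/kg on Day 1; planned dose per cycle 0.8 mg/kg (Cohort B) and 0.7 mg/kg (others). Weight is taken as constant, so ratios in mg equal ratios in mg/kg.

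**Plan's own figure.** 0.4 + 0.2 + 0.2 = 0.8 mg/kg. The per-cycle figure reproduces.

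**Listing version.** Let k be the last initiated cycle, with all earlier cycles complete and every due dose given.

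- QW, stop before Day 8: [0.8(k-1) + 0.4] / 0.8k = 1 - 0.5/k
- QW, stop between Day 8 and Day 15: [0.8(k-1) + 0.6] / 0.8k = 1 - 0.25/k
- Q3W, stop at either time: 0.7k / 0.7k = 100%

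| Last cycle k | QW, stop before Day 8 | QW, stop Day 8 to 15 | Q3W, fully dosed |
|---|---|---|---|
| 1 | 50.0% | 75.0% | 100% |
| 2 | 75.0% | 87.5% | 100% |
| 3 | 83.3% | 91.7% | 100% |
| 4 | 87.5% | 93.8% | 100% |
| 5 | 90.0% | 95.0% | 100% |
| 6 | 91.7% | 95.8% | 100% |

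**Weekly version**, reading duration of dosing as the defined treatment duration. QW, k=3, only Day 1 given in cycle 3, no delays: actual 2.0/9 = 0.222 and planned 0.8/3 = 0.267 mg/kg per week, ratio 83.3%. Without delays every entry matches the table. Here Q3W is not protected from delays: with two full cycles and the second one day late, duration is ceiling(43/7) = 7 weeks, so (1.4/7)/(0.7/3) = 85.7%.

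**When scans fall.** Scans are due every 6 weeks ± 1 week from Cycle 1 Day 1 (Protocol 8.14). Without delays, C2D15 is Day 36, C3D1 is Day 43 and C3D8 is Day 50, so the first scan window is Days 36 to 50. PD acted on before C3D1 gives 100% for a compliant QW patient. PD found after the C3D1 dose and before C3D8 gives 83.3%.

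**Cohort-level size.** The documents do not give the share of QW patients who stop mid-cycle. Assume a share f, all stopping with only Day 1 given in cycle k; the mean then falls by f × 0.5/k. For f from 10% to 50%, this is 1.7 to 8.3 points at k=3 and 5 to 25 points at k=1.

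**The case against.** The strongest reply is that little depends on this figure. The first version is explicitly a by-subject listing. No endpoint, test or stopping rule uses relative dose intensity, and SAP 10.2.1 plans no formal comparison between cohorts. Regimen recommendations belonged to the IDMC on the totality of data, and Protocol 1.9 records enrolment as complete by April 2020, before this SAP version of 2021. SAP 10.4 also summarises missed, delayed and reduced doses with reasons, and SAP 10.1.2 tabulates reasons for discontinuation, so a reader can trace why a patient shows 83%. All of this stands. It limits the consequence but does not make the listed figure correct.

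Radiological stops also tend to fall near cycle boundaries when there are no delays. That stands too, but the later part of each scan window, dose delays, clinical progression, death and withdrawal can all end treatment mid-cycle.

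A reader might infer more than the documents support:

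- *That Cohort A can never fall below 100%.* This holds only for a mid-cycle stop. In the listing, a dose reduction to 0.4 mg/kg from cycle 2 of 2 gives 1.1/1.4 = 78.6%.
- *That the by-cohort summary is certainly affected.* The weekly version is not labelled a listing and sits with the summarised measures, but its duration term is not defined by that name. The effect there depends on the reading used above.
- *That every such shortfall is unrelated to tolerability.* Some mid-cycle stops will be for adverse events. What remains is that a Q3W patient stopping for the same reason on the same day carries no penalty.

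**Conclusion.** The point holds for the listing as written. A fully compliant QW patient whose treatment ends before Day 15 of the last cycle is listed at 50.0% to 95.8%, depending on cycle and day, against 100% for a fully dosed Q3W patient stopping at the same time. These values assume constant weight and complete earlier cycles. The weekly version gives the same values without delays, provided duration of dosing means the defined treatment duration.

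The effect is confined to descriptive exposure reporting. The mean shifts shown rest on an assumed 10% to 50% of mid-cycle stops and are illustrations, not estimates. The documents do not support reading this as a threat to the efficacy analysis or to the choice of regimen. Rituximab figures are unaffected, because rituximab is given on Day 1 only. The point is worth correcting because the rule distorts one regimen's figure relative to the other and the remedy is small.

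**What to change.** **Listing version.** For all cohorts, define the planned cumulative Debio 1562 dose as the sum of protocol doses scheduled on or before the earliest of PD, death or the decision to end treatment, up to Cycle 6. Keep doses skipped for unmet retreatment criteria in the denominator. A compliant QW patient then lists at 100% (for example 0.4/0.4 at k=1 and 2.0/2.0 at k=3), as a compliant Q3W patient already does.

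**Weekly version.** State that duration of dosing is the defined treatment duration, and keep that one definition in both cohorts. Set planned dose intensity to the planned cumulative dose above divided by (3 weeks × number of initiated cycles). In the k=3 example this is 2.0/9, so the ratio becomes 100%. Delays still lower the figure in either cohort.

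**Cost.** A wording change and a small programming change. The SAP rule already refers to PD and the decision to end treatment, and Protocol 5.3 has infusion dates in the eCRF. Cohort B figures rise slightly; a fully dosed Cohort A patient's listed figure does not change. The downside is that a mid-cycle stop for toxicity no longer lowers the QW figure, as is already so for Q3W. The SAP should therefore not describe the revised measure as reflecting tolerability alone; discontinuations for toxicity are shown in the discontinuation and dose-modification tables.

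A separate matter should be settled in the same edit: which schedule supplies the planned dose for a patient switched from QW to Q3W because of COVID-19. Against the Cohort B plan, each switched cycle counts as 0.7/0.8 = 87.5%.

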10.5 Pharmacokinetics

Blood samples for pharmacokinetics will be collected as outlined in [Appendix D](#)(Safety run-In and Phase II), [Appendix E](#) (Cohort A, Part 2 and 3) and [Appendix F](#) (Cohort B, Part 2 and 3).

Concentration of Debio 1562, anti-drug antibody (ADA) Debio 1562, Debio 1562 total antibody (TAb), DM1 Free, DM1-SMCC-lysine, DM1-SMCC, Rituximab, and ADA Rituximab will be summarized by cohort and per visit and also by regimen. The following summary statistics will be produced: the number of non-missing values, the arithmetic mean, the standard deviation, the coefficient of variation, the median, the first and third quartiles, the minimum, the maximum, the geometric mean, the geometric standard deviation and the geometric coefficient of variation.

[figure not shown]
Concentrations that are below the limit of quantification will be handled as follows:

- All pre-dose concentrations observed before cycle 1 day 1 that are below the limit of quantification will be imputed by:

- o Zero for the computation of the mean, the standard deviation, and the coefficient of variation
- o Half the limit of quantification for the computation of the geometric mean, the geometric standard deviation, and the geometric coefficient of variation
- All concentrations observed after the first dose date that are below the limit of quantification will be imputed by half the limit of quantification.

PK parameters, including but not limited to C_{max} , T_{max} , $t_{1/2}$ and AUC, will be summarized similarly as above for Debio 1562, Debio 1562 TAb, DM1 Free, DM1-SMCC-lysine, DM1-SMCC and rituximab.

The overall PK and PK/PD analyses will be described in a separate analysis plan.

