#### 2.2.2. Secondary Endpoints

- PK parameters (evaluated as deemed appropriate but not limited to):  $C_{max}$ ,  $AUC_{0-t}$ ,  $AUC_{inf}$ , terminal half-life ( $t_{1/2}$ ), CL,  $V_{ss}$ ,  $T_{max}$ , for both Debio 1562 and rituximab
- Calculation of time to event parameters:

- PFS and OS
- Time to response and duration of response
- Immunogenicity of Debio 1562: presence of human ADA

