## 10.4. Safety Analyses

AEs, concomitant medication, and results from physical examination will be listed.

AEs will also be coded with the Medical Dictionary for Regulatory Activities (MedDRA; version 19.0 or later) and summarized per System Organ Class (SOC) and preferred term.

Concomitant medications will be coded using the WHO Drug Dictionary (WHO-DD; June 1, 2012 or later version). A dictionary listing of all unique concomitant medications used in the study will be provided.

All hematology, blood chemistry, vital signs, and ECG results will be listed per patient for each assessment and descriptive statistics will be tabulated for select criteria. Changes from baseline in hematology, blood chemistry, vital signs, and ECG results will be summarized by treatment. Shifts in hematology and blood chemistry from Baseline values will be summarized. Plasma will also be evaluated for the presence of humoral responses against the humanized anti CD37 antibody component or against the DM1 component (ADA).

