3.2 Secondary Endpoints

The secondary endpoints of this study are:

- PK parameters for both Debio 1562 and rituximab (evaluated but not limited to): maximum concentration (C_{max}), area under the curve (AUC_{0-t} , AUC_{inf}), terminal half-life ($t_{1/2}$), clearance, volume of distribution at steady state (V_{ss}), and time to reach maximum concentration (T_{max});
- Efficacy time-to-event endpoints:
 - o Progression-free survival (PFS) defined as the duration between the first dose date of Debio 1562 and the date of progressive disease (PD) or death due to any cause, whichever occurs first. As this study has randomized and non-randomized parts, starting date for the calculation of PFS is set to the first dose date of Debio 1562;
 - o Time to response defined as the duration between the first dose date of Debio 1562 and the date of first objective response (PR or CR). This will be computed for responders only. As this study has randomized and non-randomized parts, starting date for the calculation of TTR is set to the first dose date of Debio 1562;
 - o Duration of response (DoR) defined as the duration between the date of first objective response (PR or CR) and the date of PD or death due to any cause, whichever occurs first. This will be computed for responders only;
 - o Overall survival (OS) defined as the duration between the first dose date of Debio 1562 and the date of death due to any cause. As this study has randomized and non-randomized parts, starting date for the calculation of OS is set to the first dose date of Debio 1562;
- Immunogenicity of Debio 1562: Presence of human anti-drug antibody.

Unless otherwise specified in subsequent sections, pharmacokinetics, [REDACTED] and immunogenicity analyses are beyond the scope of this document. They will be covered by dedicated analysis plans.

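### SAP 10.5 summarises anti-drug antibody as a concentration, with means and a half-limit substitution, although the secondary endpoint is presence of antibody to Debio 1562

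*SAP*

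**What the plan says.** The endpoint is qualitative in both documents. Protocol 2.2.2 has "Immunogenicity of Debio 1562: presence of human ADA" and SAP 3.2 has "Immunogenicity of Debio 1562: Presence of human anti-drug antibody". Protocol 10.4 describes the evaluation in the same way: "Plasma will also be evaluated for the presence of humoral responses against the humanized anti CD37 antibody component", or against the DM1 component.

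SAP 10.5 treats ADA as a measured quantity. Its list begins "Concentration of Debio 1562, anti-drug antibody (ADA) Debio 1562, Debio 1562 total antibody (TAb" and also contains ADA to rituximab. The list is summarised by cohort, visit and regimen, with "the number of non-missing values, the arithmetic mean, the standard deviation, the coefficient of variation, the median", then quartiles, extremes and the geometric counterparts. No count or percentage of positive patients is prescribed.

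The same section sets two rules for results below LLOQ. Before Cycle 1 Day 1 the substituted value is "Zero for the computation of the mean, the standard deviation, and the coefficient of variation", and half the limit for the geometric statistics. Later, "All concentrations observed after the first dose date that are below the limit of quantification will be imputed by half the limit of quantification". Neither rule excludes ADA.

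SAP 3.2 says of the wider analysis: "and immunogenicity analyses are beyond the scope of this document. They will be covered by dedicated analysis plans". That deferral yields to anything a later section of the SAP specifies.

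**The concern.** A yes/no status per patient calls for a count and a percentage, which is also the SAP's own convention for categorical data (section 9.1). Section 10.5 instead prescribes statistics suited to drug levels. A cohort mean by visit does not say how many patients developed antibody. It also cannot separate, patient by patient, antibody present before treatment from antibody that appeared on treatment. For rituximab that distinction could matter, because protocol 3.1 allows earlier anti-CD20 treatment.

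Protocol 6.2 intends to examine the effect of immunogenicity on PK, safety and anti-tumour activity, and that work needs each patient's ADA status. The substitution rule adds a second problem: it can put a positive number in the table where no antibody was found.

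**Working it through.** The documents give no figure for ADA that could be reproduced, so the check applies the SAP 10.5 rules to simple cases.

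**Inputs**

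- Statistics and substitution rules: SAP 10.5.
- Endpoint: protocol 2.2.2 and SAP 3.2.
- LLOQ of the ADA assay: not given. Call it L, any positive value.
- Coding of a negative result: not given. Assume it is reported as below LLOQ.
- Cohort sizes of 10, 15 and 30: illustrative.

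**Step 1. Cohort with no ADA, after the first dose.** Every value becomes L/2.

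- Arithmetic mean = n × (L/2) / n = L/2
- Geometric mean = exp(ln(L/2)) = L/2
- SD = 0 and CV = 0%

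This holds for any n and any L.

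**Step 2. Same cohort, under the rule for samples before Cycle 1 Day 1.**

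- Arithmetic mean = 0
- Geometric mean = L/2

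The arithmetic mean therefore moves from 0 to L/2 although no patient has antibody. The geometric mean does not move.

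This contrast requires the baseline ADA sample to fall under the first rule. Protocol 6.2 and Appendix E place that sample pre-dose on Day 1 of Cycle 1. Read literally, that is neither before Cycle 1 Day 1 nor after the first dose date, so the wording leaves its handling open.

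**Step 3. What the table should convey for that cohort.** The incidence is 0/n = 0%. The upper limit of the exact two-sided 95% interval is 1 − 0.025^(1/n):

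| n | Incidence | Upper limit |
|---|---|---|
| 10 | 0% | 30.8% |
| 15 | 0% | 21.8% |
| 30 | 0% | 11.6% |

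A mean of L/2 with SD 0 conveys neither the zero nor its uncertainty.

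**Step 4. Does the mean identify incidence?** Take n = 30 and L = 1, so each negative contributes 0.5.

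- One positive at 10.0: (10.0 + 29 × 0.5)/30 = 24.5/30 = 0.817; incidence 1/30 = 3.3%.
- Ten positives at 1.45: (10 × 1.45 + 20 × 0.5)/30 = 24.5/30 = 0.817; incidence 10/30 = 33.3%.

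The arithmetic mean is the same while the incidence differs tenfold. The geometric means differ (0.553 and 0.713), but neither converts to a proportion.

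**Step 5. The other coding.** If a negative is recorded without a number, the substitution rule does not reach it. The mean then describes positive samples only, and n counts those samples at that visit without a denominator. The artefact in steps 1 and 2 disappears, but the proportion of patients with ADA is still not reported.

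**The case against.** Four points can be made for the plan.

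First, a reader might infer that the trial has no plan to report ADA incidence. The documents do not support that. SAP 3.2 sends immunogenicity to dedicated plans that are not among the documents reviewed, and protocol 10.4 states the qualitative evaluation. The SAP's numbering also passes from 10.5 to 10.7, so a section may have been removed before publication. This point stands: the missing incidence cannot be counted as an error. It does not rescue the table in 10.5. The deferral gives way to later sections, 10.5 is such a section, and its closing deferral covers only PK and PK/PD. The concentration summary of ADA therefore remains a planned output.

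Second, a reader might infer that every negative sample yields a positive mean. The rule concerns concentrations below a limit, and nothing says that a negative ADA result is recorded that way. Before treatment, the value entering the arithmetic mean is zero. The effect is therefore post-dose and conditional on coding. The mismatch with the endpoint does not depend on coding.

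Third, ADA to rituximab is not part of the stated endpoint, so the mismatch argument applies only to ADA to Debio 1562. The unsuitable statistics and the substitution rule nevertheless apply to both.

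Fourth, the table is descriptive and supports no decision rule. That is correct and limits the weight of the point.

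**Conclusion.** The point holds in limited form. SAP 10.5 prescribes a summary of ADA that does not estimate presence of ADA to Debio 1562, whichever way negatives are coded. If negatives are coded below LLOQ, the post-dose mean in a cohort free of ADA is LLOQ/2 with SD 0. If, in addition, the baseline sample follows the pre-treatment rule, the arithmetic mean appears to rise from 0. The size of that false rise is half of a limit that the documents do not state.

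Whether incidence is reported properly elsewhere cannot be judged from these documents. No hypothesis test, sample size or error rate is affected. The risk is a misleading table for a descriptive secondary endpoint.

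**What to change.** Remove ADA to Debio 1562 and ADA to rituximab from the concentration list in SAP 10.5, and state that the below-LLOQ rule does not apply to ADA. Then take one of two routes:

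1. Tabulate by cohort, separately for each antibody, the number and percentage of patients who are ADA-positive at baseline, newly positive after baseline, and positive at any time. For newly positive patients, use as denominator those with a baseline result and at least one post-baseline result. Summarise or list titres, if measured, for positive samples only.
2. Delete ADA from 10.5 and cross-refer to the dedicated immunogenicity plan, after confirming that it contains that table.

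Either route should state how a negative result is recorded and that the pre-dose sample on Cycle 1 Day 1 is the baseline. The cost is a few lines of SAP text and simpler tables; no additional samples or visits are needed.
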